1.1 Background Information

1.1.1 Rationale for Proposed Clinical Study

Agonists of the S1P₁ receptor block lymphocyte migration out of the lymph tissue through internalization of the receptor, resulting in a sequestration of lymphocytes ¹⁵. Recent clinical development of S1P₁ receptor agonists and the resulting lymphocyte sequestration have potential for treating multiple autoimmune and chronic inflammatory diseases including multiple sclerosis, IBD and psoriasis. Fingolimod was the first drug in this class to be approved for the treatment of multiple sclerosis ¹⁶. More recently the S1P₁ receptor agonist ponesimod was observed to reduce the severity of chronic plaque psoriasis after chronic oral administration in a Phase 2 randomized clinical trial ¹⁷. In this study, ponesimod was associated with dyspnea, elevated liver enzymes, bradycardia, headache and dizziness. Furthermore, S1P₁ agonists (FTY720, SEW2871) have been observed to have an anti-inflammatory impact on the production of IL-12 family cytokines, indicating therapeutic potential for S1P treatment of several inflammatory diseases like psoriasis ¹⁸. Importantly, a recent report demonstrating S1P₄ agonists inhibition of plasmacytoid dendritic cell activation and interferon-alpha production suggest a potential therapeutic role for S1P₁/S1P₄ agonists like etrasimod in paradoxical psoriasis ¹⁹.

In addition to the potential anti-inflammatory benefits of systemic lymphocyte immunomodulation, S1P is known to exert anti-proliferative effects in human keratinocytes ²⁰, and inhibits dendritic cell migration ²¹. Thus, the potential role of S1P receptor modulation in skin-EIMs of IBD might involve both systemic and local epidermal mechanisms.

Histopathology of ulcerative PG is characterized by a dense dermal infiltrate composed mainly of neutrophils in biopsy from the central area of ulceration, and a mainly lymphocytic infiltrate with thrombosis of vessels and extravasated erythrocytes in biopsy from the border of the ulcer ². In patients with ulcerative PG the number of T-lymphocytes are significantly higher at the wound edge compared to the wound bed. In contrast, neutrophils were significantly more numerous in the wound bed than the wound edge ³. This suggests that activated T-lymphocytes at the wound edge could promote ulcer formation. Further support for T-cell involvement in the disease comes from observations in PG patients that are characterized by an over-expression in the blood of

the CD4+CCR5+ and CD4+CCR6+ and a down-regulation of CD4+CCR4+ counts with respect to healthy subjects ⁴.

[figure not shown]
In addition, a differentiated profile for etrasimod compared to other S1P modulators for the treatment of PG could arise from the hypothesis that S1P₄ as well as S1P₁ receptor modulation could aid in neutrophil trafficking ⁵.

Together, this evidence suggests that T-lymphocytes can play a role in PG and that reduction of lymphocytes by S1P₁ receptor modulators like etrasimod may represent a novel therapeutic approach in PG.

[figure not shown]
The aim of the proposed clinical study is to evaluate the role of S1P modulation in the setting of active cutaneous PG. Next generation S1P modulators such as etrasimod with improved side effect profiles may represent a novel therapy for PG patients.

[figure not shown]
1.1.2 Summary of Preclinical Data

[figure not shown]
1.1.2.1 Pharmacology

[figure not shown]
1.1.2.2 Nonclinical Safety

[figure not shown]

[figure not shown]

1.1.3 Summary of Clinical Data

1.2 Ethics and Regulatory Considerations

The study will be conducted in compliance with the International Conference on Harmonization (ICH) Guidelines for Good Clinical Practice (GCP), Title 21 of the United States (US) Code of Federal Regulations (CFR) Part 50 (21CFR §50 (Protection of Human Subjects), 21 CFR §56 (Institutional Review Boards [IRB]), and 21 CFR §312 (Investigational New Drug) and applicable regulatory requirements, the study protocol, and where applicable, sponsor and/or Contract Research Organization (CRO) Standard Operating Procedures (SOPs). The protocol and informed consent will be submitted for consideration by the appropriate IEC and written approval from the Chair or designated deputy of the IEC is required before clinical activities of the study can commence.

The IEC must be notified promptly by the investigator of the following:

- Deviations from, or changes in, the protocol to eliminate immediate hazards to the trial participants
- Changes increasing the risk to participants and/or affecting significantly the conduct of the trial
- All AEs that meet the definition of a SAE if according to the local law and regulation
- New information that may adversely affect the safety of the participants during the conduct of the trial.

Any changes to the protocol will be made by means of a formal written protocol amendment. All amendments will require IEC approval before implementation except when changes to the protocol are required immediately to eliminate hazards to the volunteer or when the changes involve only logistical or administrative aspects of the trial (for example, change of medical monitor, change in telephone number, etc.).

2 STUDY OBJECTIVES

2.1 Objectives

Efficacy

- To evaluate the efficacy of etrasimod (APD334) in patients with PG over a 12-week treatment period.

Safety

- To assess the safety and tolerability of etrasimod (APD334) in patients with PG over a 12-week treatment period.

[figure not shown]
3 INVESTIGATIONAL PLAN

3.1 Overall Study Design and Plan

This is a Phase 2a, open label, proof-of-concept clinical study to assess the efficacy and safety of etrasimod (APD334) in patients with PG. The trial will include adult patients, 18-80 years of age with active PG ulcers.

All visits in the study are ambulatory visits. The screening period will last up to 4 weeks and will be followed by a 12-week treatment period. During the treatment period, patients will need to take 1 tablet of study medication once per day. The last dose is planned to be taken one day before the end of the treatment period at Week 12. A follow-up visit will take place 2 weeks after the end of treatment.

Figure 1 Study Design

The study will consist of the following periods:

Screening Period (up to 4 weeks before baseline visit):

Each patient will be asked to visit the study site for screening assessments within 4 weeks prior to the planned start of the treatment (Day 1). All patients must be consented before any study specific procedure is performed and written informed consent must be obtained. Patients will then undergo screening procedures to determine eligibility.

[REDACTED]

Treatment Visits:

Baseline Visit (Day 1): Patients will return to the study site to receive the first dose of the study medication. Patients should be instructed to take their tablet as a first thing in the morning on an empty stomach. Patients should be advised not to crush, break, chew, or dissolve the tablet and to take study medication with water. The patients will remain at the study site for at least 6 hours for safety evaluation (please refer to the [REDACTED])

[REDACTED]

Visits Week 2, Week 4, Week 8, and Week 12: Patients will return to the study site and perform all planned examinations as described in [REDACTED]. Last dose of study medication is planned 1 day before the end of the treatment visit at Week 12.

Follow up Visit/End of Study Visit:

[figure not shown]
Visit Week 14, 2 weeks after end of treatment: Patients will return to the study site for the final visit, and final procedures will be performed per [REDACTED]

[figure not shown]
Premature Discontinuation: All procedures planned for Week 12 visit should be performed for all patients that discontinue the study prematurely.

3.2 Study Duration and Dates

The study duration will be up to 18 weeks per patient. This will include up to 4 weeks for screening, followed by a 12-week treatment period and a follow-up visit 2 weeks after the end of treatment.

[REDACTED]

4 STUDY POPULATION

The study population will consist of eight (8) patients with PG who fulfill eligibility (inclusion & exclusion) criteria.

4.1 Inclusion and Exclusion Criteria

Each patient must meet the inclusion and exclusion criteria described below to be enrolled in the study.

4.1.1 Inclusion Criteria

1. Male or female of age 18 to 80 years (inclusive) at the time of screening.
2. Able to provide a signed informed consent prior to any study related procedure being conducted and willing and able to comply with the study requirements.
3. Diagnosis of PG with active, non-healing ulcer.
4. Considered to be in stable health in the opinion of the investigator as determined by:
 - a.) A screening physical examination with no clinically significant abnormalities unrelated to PG.
 - b.) Vital signs at screening: pulse rate \geq 55 bpm, systolic blood pressure (SBP) \geq 90 mmHg, and diastolic blood pressure (DBP) \geq 55 mmHg.
 - c.) Liver function tests (alanine aminotransferase [ALT]/aspartate aminotransferase [AST], bilirubin and alkaline phosphatase) $<$ 2x the upper limit of normal (ULN).
 - d.) All other pre-study clinical laboratory findings within normal range, or if outside of the normal range are not deemed clinically significant in the opinion of the investigator with exemption to leucopenia and lymphopenia – please refer to exclusion criterion #24.
 - e.) No clinical abnormalities noted in the 12-lead ECG in the opinion of the investigator (Refer also to exclusion criterion #13).
 - f.) No evidence of macular edema in an ophthalmology evaluation (performed by an ophthalmologist), supported with optical coherence tomography (OCT), where available (dependent on site capability) no later than 3 months prior to screening.
5. Eligible male and female patients must agree not to participate in a conception process (i.e. active attempt to let female partner to become pregnant or to impregnate, sperm donation, oocyte donation, in vitro fertilization) for at least 30 days after the last dose of study drug.

Female patients who are sexually active with non-sterile male partner must be:

- a.) non-pregnant (evidenced by a negative serum human chorionic gonadotropin (hCG) pregnancy test at screening and a urine dipstick pregnancy test at Day 1)
- b.) non-lactating
- c.) one of the following:
 - either sexually abstinent (if this is the preferred and usual lifestyle of the individual). Periodic abstinence (calendar, symptothermal, post-ovulation methods), withdrawal (coitus interruptus), and lactational amenorrhoea methods are not acceptable

- or surgically sterile (surgical sterility prior to screening for at least 6 months for tubal ligation performed laparoscopically, hysterectomy and/or bilateral oophorectomy)
- or postmenopausal (at least 2 years without menses)
- or agree to continue to use an accepted method of birth control. Patients should be consistently using the hormonal contraceptive for at least 1 month (30 days) prior to screening, during the study and for at least 30 days after last study medication administration

Acceptable methods of birth control are:

- combined (estrogen and progestogen containing) hormonal contraception associated with inhibition of ovulation
 - oral
 - intravaginal
 - transdermal
- progestogen-only hormonal contraception associated with inhibition of ovulation
 - oral
 - injectable
 - implantable
- intrauterine device (IUD)
- intrauterine hormone-releasing system (IUS)

Contraceptive measures, such as Plan B (used after unprotected sex), are not acceptable methods of contraception for this study.

Eligible male patients will either be:

- surgically sterile (i.e., vasectomy), for at least 3 months (90 days) prior to screening
- or
- when sexually active with a female partner, the partner must be either surgically sterile, postmenopausal, or agree to continue to use an accepted method of birth control during and for at least 30 days after last study medication administration as defined in 7 above. Please note that the use of condoms alone or double barrier and use of spermicide are not an acceptable method of contraception for this study.

4.1.2 Exclusion criteria

1. Clinically significant infection (e.g., pneumonia, pyelonephritis) as judged by the investigator with an end date less than 6-weeks prior to treatment start (Day 1). In case of infection requiring hospitalization or intravenous antimicrobial therapy, or opportunistic infection, this infection must have ended at least 8 weeks prior to Day 1.

2. Infection with hepatitis C virus anytime in the past; confirmed active infection with hepatitis B virus at screening.
3. History of severe renal or severe hepatic impairment.
4. Current active or latent tuberculosis (TB), regardless of treatment history or history of TB that has not been successfully treated
5. A positive diagnostic TB test at screening defined as a positive QuantiFERON[®] test or 2 successive indeterminate QuantiFERON[®] tests
6. Exposure to B-cell or T-cell targeted therapies (such as natalizumab, rituximab, abatacept) within 5 half-lives prior to Day 1.
7. Other immunosuppressive, immunomodulating or antineoplastic agents not listed in Section 6.13.1 or not meeting the stability time period for concomitant medications indicated as permitted in Section 6.13.
8. Receipt of any investigational agent within 30 days or 5 half-lives (whichever is longer), prior to Day 1.
9. Use of moderate to strong inhibitors of CYP2C9 (e.g., amiodarone, felbamate, fluconazole, miconazole, piperine).
10. Abnormal forced expiratory volume (FEV₁) or forced vital capacity (FVC) i.e., < 80% of predicted values at screening.
11. Any known history of congenital or acquired immuno-deficiency (e.g., common variable immunodeficiency, human immunodeficiency virus [HIV] infection [ELISA and Western blot] test result, organ transplantation).
12. Recent history (within 6 months of screening assessments) of cardio- or cerebrovascular disease, acute coronary syndrome (ACS), myocardial infarction (MI), unstable angina, cerebro-vascular accident, including transient ischemic attack (TIA).
13. History or presence of cardiac arrhythmia, conduction system disease (including AV node dysfunction, 2nd or 3rd degree heart block, and sick sinus syndrome), or use of Class Ia or Class III anti arrhythmic agents, or baseline QTc \geq 500 msec.
14. Congestive heart failure (NYHA III or NYHA IV).
15. Any surgical procedure requiring general anesthesia within 30 days prior to Day 1 or plans to undergo major surgery during the study period.
16. History of retinal macular edema.
17. History of or signs and symptoms of progressive multifocal leukoencephalopathy (PML) as assessed by the PML checklist at screening.
18. History of more than one episode of herpes zoster or any episode of disseminated zoster.
19. Patients without documented positive varicella zoster virus (VZV) IgG-antibody status or patients who have not completed VZV vaccination within 6 weeks prior to Day 1.
20. Receipt of live vaccine within 6 weeks prior to Day 1.

21. History of lymphoproliferative disorder, lymphoma, leukemia, myeloproliferative disorder, or multiple myeloma.
22. History of malignancy except for adequately treated basal cell skin cancer and in situ carcinoma of the cervix of the uterus that have been completely excised with documented, clear margins.
23. History of severe allergic or anaphylactic reactions requiring medical attention.
24. Leukopenia or lymphopenia at screening;
25. Current or recent history (within 1 year prior to Day 1) of alcohol dependence or illicit drug use.
26. Active psychiatric problems that, in the investigator's opinion, may interfere with compliance with the study procedures.
27. History of any other clinically significant medical condition that, in the investigator's opinion, would preclude patient from safe participation in the study.
28. Inability to attend all the study visits or comply with study procedures.
29. Prior exposure to etrasimod (APD334) or prior participation in any study of etrasimod (APD334).

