| Inclusion Criteria: | 
 1. Male or female of age 18 to 80 years (inclusive) at the time of screening. 2. Able to provide a signed informed consent prior to any study related procedure being conducted and willing and able to comply with the study requirements. 3. Diagnosis of PG with active, non-healing ulcer. 4. Considered to be in stable health in the opinion of the investigator, as determined by: 
 a.) A screening physical examination with no clinically significant abnormalities unrelated to PG. b.) Vital signs at screening: pulse rate \geq 55 bpm, systolic blood pressure (SBP) \geq 90 mmHg, and diastolic blood pressure (DBP) \geq 55 mmHg. c.) Liver function tests (alanine aminotransferase [ALT]/aspartate aminotransferase [AST], bilirubin and alkaline phosphatase) $<$ 2x the upper limit of normal (ULN). d.) All other pre-study clinical laboratory findings within normal range, or if outside of the normal range are not deemed clinically significant in the opinion of the investigator with exemption to leucopenia and lymphopenia – please refer to exclusion criterion #24. e.) No clinical abnormalities noted in the 12-lead electrocardiogram (ECG) in the opinion of the investigator (Refer also to exclusion criterion #13). f.) No evidence of macular edema in an ophthalmology evaluation (performed by an ophthalmologist), supported with optical coherence tomography (OCT), where available (dependent on site capability) at screening. 5. Eligible male and female patients must agree not to participate in a conception process (i.e. active attempt to let female partner to become pregnant or to impregnate, sperm donation, oocyte donation, in vitro fertilization) for at least 30 days after the last dose of study drug. 
Female patients who are sexually active with non-sterile male partner must be:
 
 a.) non-pregnant (evidenced by a negative serum human |

| | |
|--|---|

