6.13.2 Excluded Medications

The following medications are excluded prior or during the study:

- Exposure to B-cell or T-cell targeted therapies (such as natalizumab, rituximab, abatacept) within 5 half-lives prior to Day 1
- Other immunosuppressive, immunomodulating or antineoplastic agents or other monoclonal antibody / biologic not listed in the Permitted Medications within 5-half-lives prior to Day 1 (small molecules) or 60 days prior to D1 (biologics).
- All live vaccines within 6 weeks prior to Day 1, during study treatment and for at least 6 months after the last dose of study drug
- Moderate to strong inhibitors of CYP2C9 (e.g., amiodarone, felbamate, fluconazole, miconazole, piperine). within 5-half-lives prior to Day 1, during the study and for 2 weeks after the last intake of study medication
- Other routes for systemic corticosteroids (IM and IV)
- Class Ia or Class III anti-arrhythmic agents
- Any other medication which in the opinion of the investigator would affect the suitability of the patient to continue in the study, interfere with interpretation of study results or affect compliance with the protocol requirements
- Receipt of any investigational agent within 30 days or 5 half-lives (whichever is longer), prior to Day 1.

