10.2 Protocol Interpretation and Compliance

To ensure accurate interpretation and implementation of the study, the procedures and endpoints defined in the protocol will be carefully reviewed by the PI and his or her staff prior to the time of study initiation. The sponsor and PI will follow all reasonable means to resolve any differences of opinion of matters of eligibility, toxicity and other endpoints. In the event that a resolution cannot be reached then one or both parties may seek to terminate the study following the provisions outlined in the Clinical Trials Agreement.

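### Two eligibility criteria need reconciling: the eye-examination window in inclusion 4f differs between synopsis and body, and exclusion 19, as written, excludes VZV IgG-positive patients who have not completed vaccination

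*Combined protocol and SAP*

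**What the plan says.** **Inclusion 4f.** An ophthalmologist's evaluation, supported by OCT, must show no macular edema. The sentence is the same in both places until its ending. In the synopsis it ends "where available (dependent on site capability) at screening"; in Section 4.1.1 it ends "where available (dependent on site capability) no later than 3 months prior to screening". Section 6.3.2 explains that the examination is meant both to exclude and to follow retinal disease, and leaves its timing to a schedule that is redacted in the public copy. Section 4.1 makes the criteria listed in the body the condition of enrolment.

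**Exclusion 19.** The wording is identical in the synopsis and Section 4.1.2. It removes patients lacking documented positive VZV "IgG-antibody status or patients who have not completed VZV vaccination within 6 weeks prior to Day 1". The first limb is thus the missing antibody proof; the second limb, joined by *or*, is the vaccination condition. Section 6.8.2 has VZV IgG measured at screening and at no other time, and Section 3.1 limits screening to 4 weeks.

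**Neighbouring text.** Exclusion 20 is "Receipt of live vaccine within 6 weeks prior to Day 1", and Section 6.13.2 lists the same restriction: "All live vaccines within 6 weeks prior to Day 1, during study treatment". For the more serious infections, exclusion 1 says "this infection must have ended at least 8 weeks prior to Day 1". Section 10.2 asks the sponsor and the principal investigator to "resolve any differences of opinion of matters of eligibility, toxicity and other endpoints", without giving a rule for doing so.

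**The concern.** The two versions of 4f set different windows for the same safety examination. Because Section 4.1 binds sites to the body list, the wider and less clearly worded version is the operative one, and the synopsis describes a stricter rule than the one that applies. At stake is how recent the retinal baseline is when a patient takes the first dose.

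Exclusion 19 has a different fault. Its two texts agree with each other, but the logic gives a result that is unlikely to be meant: a patient with proven VZV antibodies is excluded for not having completed vaccination. About six centers must apply this criterion. A site that follows the words and a site that follows the probable intent would decide differently on the same patient, and in a study of 8 each patient is one-eighth of the sample.

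**Working it through.** The plan gives no figure of its own to reproduce here. The check is a comparison of texts with some calendar arithmetic.

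**1. Age of the eye examination at Day 1 under 4f**

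Inputs: screening of up to 4 weeks = 28 days (Section 3.1); three calendar months = 89–92 days (89 when they cover a 28-day February, March and April).

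- Synopsis: maximum age = length of screening = 28 days = 4 weeks.
- Body, read as not older than 3 months: maximum age = 3 months + screening = 89 + 28 = 117 days to 92 + 28 = 120 days, that is 117/7 = 16.7 to 120/7 = 17.1 weeks.
- With only 7 days of screening: 7 days against 96–99 days. The gap is 89–92 days in either case.
- Body, read literally: the examination must lie 3 months or more before screening, with no upper limit. That cannot be intended, given the purpose stated in Section 6.3.2.

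An examination done at screening meets both versions in their likely sense.

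**2. Logic of exclusion 19**

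The table shows who gets past item 19 alone, for each reading of the connector and of the six-week phrase.

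| VZV IgG | Vaccination completed | As written (*or*), inside last 6 weeks | As written (*or*), at least 6 weeks before | Either proof suffices, inside last 6 weeks | Either proof suffices, at least 6 weeks before |
|---|---|---|---|---|---|
| Positive | No | excluded | excluded | passes | passes |
| Positive | Inside last 6 weeks | passes | excluded | passes | passes |
| Positive | More than 6 weeks before | excluded | passes | passes | passes |
| Negative | No | excluded | excluded | excluded | excluded |
| Negative | Inside last 6 weeks | excluded | excluded | passes | excluded |
| Negative | More than 6 weeks before | excluded | excluded | excluded | passes |

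With the connector as written, the IgG-positive patient without vaccination is excluded on either timing. Every IgG-negative patient is also excluded, so the vaccination limb lets nobody in. Only the either-proof reading admits the unvaccinated IgG-positive patient.

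**3. Timing of exclusion 19**

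Exclusion 20 uses the same six-week phrase for the period just before Day 1, while exclusion 1 uses different words when a minimum interval is meant. The protocol's own usage therefore points to the last 6 weeks. The two readings are alternatives, and each has a difficulty:

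- *Inside the last 6 weeks.* If the vaccine is live (an assumption; the documents do not say), meeting the vaccination limb of item 19 triggers exclusion 20 and Section 6.13.2. With the *or* as written, items 19 and 20 together would then admit nobody. If the vaccine is not live, there is no clash.
- *At least 6 weeks before.* 6 weeks = 42 days; screening is at most 28 days; 42 > 28. A patient first found IgG-negative at screening could not meet the interval in the same screening period without rescreening, which no visible text mentions. This matters only under the either-proof reading.

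**The case against.** The strongest reply is that the practical effect is small or unproven. Section 6.3.2 sends the timing of the eye examination to a redacted schedule; if that schedule requires an examination at screening, the 117–120 day ceiling never arises. That is correct, and the figure is only an upper bound. The two texts of 4f would still disagree. A history of macular edema is excluded separately by item 16, but that does not replace a current examination.

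On exclusion 19, sites would probably take either proof as sufficient, and IgG testing at screening fits that reading. What then remains is possible wrongful exclusion of an unknown number of patients in an exploratory study. This is fair: taken literally, the item errs towards exclusion, and no unsafe admission through it is claimed. But no readable text states the either-proof rule, and the route in Section 10.2 supplies none.

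The live-vaccine clash and the 42-day point are also conditional, and they rest on opposite readings of one phrase, so both cannot hold. That stands too. They show that neither timing is free of difficulty, but the conclusion does not depend on them. Lastly, only 4f is a contradiction between two places; exclusion 19 is one faulty wording used twice.

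**Conclusion.** The concern holds, and the criteria should be fixed. Two points need no assumption: the versions of 4f set different windows, and exclusion 19, followed exactly, excludes IgG-positive patients who have not completed vaccination while leaving IgG-negative patients no way in.

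For 4f the size is at most 28 days under the synopsis against an upper bound of 117–120 days under the body. That bound assumes that the body means not older than 3 months, that screening takes the full 4 weeks, and that the redacted schedule does not require an examination at screening. For exclusion 19 the number of patients affected cannot be estimated from the documents. Confidence is high for the textual defects; the practical size is conditional. No endpoint, analysis or sample-size figure changes.

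**What to change.** Issue one clarifying amendment that:

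1. states a single, identically worded examination window in synopsis 4f, Section 4.1.1 item 4f and the schedule of procedures;
2. rewords exclusion 19 in the synopsis and Section 4.1.2 so that it is explicit whether the two conditions are alternatives or both required, and whether the 6 weeks is a recent period or a minimum interval;
3. checks the new wording against exclusion 20, Section 6.13.2 and the 4-week screening period.

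The clinical rule and the intervals are for the sponsor's medical team to decide; the request is only that the passages be reconciled. The cost is a short amendment to two criteria in two places, with possibly a repeat eye examination for some patients, depending on the window chosen. Design, sample size and analysis stay as they are.
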